18.5 Blinded Central Review of Primary Endpoint

The blinded review will be conducted by the Study Chairs, and representatives from the SWOG Statistics and Data Management Center, Oncology Nursing Professionals Committee, and Committee Leadership. The blinded review will be facilitated by provision to the review team of all patient chart information pertaining to the primary endpoint. Identifying information about patient identifiers and treatment assignment will be abstracted, the information will be compiled into a single PDF for each patient, and transmitted to the reviewers in encrypted, password protected electronic files. The blinded review will occur at the completion of study follow-up.

18.6 Approved Antiviral Therapies in Adults

Drug	Dose in Adults*	Use in Children*	Pregnancy Category†	Potential Side Effects†	Monitoring on Treatment‡
Preferred					
Peg-IFN- α -2a (adult) IFN- α -2b (children)	180 mcg weekly	; \geq 1 year dose: 6 million IU/m ² three times weekly [§]	C	Flu-like symptoms, fatigue, mood disturbances, cytopenia, autoimmune disorders in adults, anorexia and weight loss in children	Complete blood count (monthly to every 3 months) TSH (every 3 months) Clinical monitoring for autoimmune, ischemic, neuropsychiatric, and infectious complications
Entecavir	0.5 mg daily ^k	; \geq 2 years dose: weight-based to 10-30 kg; above 30 kg: 0.5 mg daily ^k	C	Lactic acidosis (decompensated cirrhosis only)	Lactic acid levels if there is clinical concern Test for HIV before treatment initiation
Tenofovir dipivoxil fumarate	300 mg daily	; \geq 12 years	B	Nephropathy, Fanconi syndrome, osteomalacia, lactic acidosis	Creatinine clearance at baseline If at risk for renal impairment, creatinine clearance, serum phosphate, urine glucose, and protein at least annually Consider bone density study at baseline and during treatment in patients with history of fracture or risks for osteopenia Lactic acid levels if there is clinical concern Test for HIV before treatment initiation
Tenofovir alafenamide	25 mg daily	—	There are insufficient human data on use during pregnancy to inform a drug-associated risk of birth defects and miscarriage.	Lactic acidosis	Lactic acid levels if clinical concern Assess serum creatinine, serum phosphorus, creatinine clearance, urine glucose, and urine protein before initiating and during therapy in all patients as clinically appropriate Test for HIV before treatment initiation
Nonpreferred					
Lamivudine	100 mg daily	; \geq 2 years dose: 3 mg/kg daily to max 100 mg	C	Pancreatitis Lactic acidosis	Amylase if symptoms are present Lactic acid levels if there is clinical concern Test for HIV before treatment initiation
Adefovir	10 mg daily	; \geq 12 years	C	Acute renal failure Fanconi syndrome Lactic acidosis	Creatinine clearance at baseline If at risk for renal impairment, creatinine clearance, serum phosphate, urine glucose, and urine protein at least annually Consider bone density study at baseline and during treatment in patients with history of fracture or risks for osteopenia Lactic acid levels if clinical concern
Telbivudine	600 mg daily	—	B	Creatine kinase elevation and myopathy Peripheral neuropathy Lactic acidosis	Creatine kinase if symptoms are present Clinical evaluation if symptoms are present Lactic acid levels if there is clinical concern

* Dose adjustments are needed in patients with renal dysfunction.

†In 2015, the U.S. Food and Drug Administration replaced the pregnancy risk designation by letters A, B, C, D, and X with more specific language on pregnancy and lactation. This new labeling is being phased in gradually, and to date only TAF includes these additional data.

‡Per package insert.

§Peg-IFN-a-2a is not approved for children with chronic hepatitis B, but is approved for treatment of chronic hepatitis C. Providers may consider using this drug for children with chronic HBV. The duration of treatment indicated in adults is 48 weeks.

¶Entecavir dose is 1 mg daily if the patient is lamivudine experienced or if they have decompensated cirrhosis.

Abbreviation: TSH, thyroid stimulating hormone.

<https://aasldpubs.onlinelibrary.wiley.com/doi/pdfdirect/10.1002/hep.29800>

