3.1 Entecavir (ETV)

a. PHARMACOLOGY

Mechanism of Action:

Entecavir is a guanosine nucleoside analogue. The phosphorylated active form inhibits the activity of hepatitis B virus (HBV) polymerase in base priming, reverse transcription of the negative strand pregenomic messenger RNA, and synthesis of the positive strand of HBV DNA.

b. PHARMACOKINETICS

1. Absorption:

The peak plasma concentration (C_{max}) of entecavir is achieved in 0.5 to 1.5 hours at doses ranging between 0.1 and 1 mg, and the steady state is achieved in 6 to 10 days. Both C_{max} and area under the concentration-time curve (AUC) at steady state increases proportionally to increasing doses of entecavir. The oral tablet and the oral solution have a bioavailability ratio of 1:1 and may be used interchangeably.

Co-administration of entecavir with food has been shown to delay absorption, decrease C_{max} by 44 to 46%, and decrease AUC by 18 to 20%. Entecavir should be administered at least 2 hours before or after a meal.

2. Distribution:

Pharmacokinetic studies have shown that entecavir distributes extensively into tissues and have an approximate protein binding of 13%.

3. Metabolism:

Entecavir is not metabolized by the cytochrome P450 enzymes, and it does not inhibit or induce the P450 enzymes.

4. Elimination:

Entecavir is mainly eliminated by the kidneys as 62 to 73% unchanged drug through glomerular filtration and net tubular secretion. The half-life of entecavir is approximately 128 to 149 hours, and the renal clearance ranges between 360 to 471 mL/min.

c. ADVERSE EFFECTS

1. Possible Side Effects of *Entecavir*:

Refer to the current FDA-approved package insert for the most comprehensive and up to date information on adverse reactions.

Adverse effects reported in > 10% of subjects treated with entecavir include elevated alanine aminotransferases.

Adverse effects reported in 1% to 10% of subjects include: headache, fatigue, skin rash, hematuria, glycosuria, hyperglycemia, abdominal pain, nausea, vomiting, diarrhea, unpleasant taste, elevated serum lipase, bilirubin, and creatinine.

Serious adverse effects reported in < 1% of subjects include: anaphylactoid shock, hepatomegaly with steatosis, lactic acidosis, macular edema, and thrombocytopenia.

2. Pregnancy and Lactation:

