There is insufficient data from human studies to adequately assess the risk of using entecavir during pregnancy (including the risks of birth defects, miscarriage or adverse maternal or fetal outcomes). Animal studies in rats and rabbits have shown evidence of embryofetal toxicity and maternal toxicity at doses above the maximum recommended human dose. The use of entecavir should be avoided in pregnant women, as there are other agents available. For those who are pregnant and have been exposed to entecavir, a pregnancy registration is available to monitor fetal outcomes.

Entecavir has been found in the milk of rats, but its presence is unknown in human milk. Breast-feeding mothers should avoid taking entecavir.

3. Drug Interactions:

Coadministration of ETV with drugs that reduce renal function or compete for active tubular secretion may alter the pharmacokinetic or pharmacodynamics properties of ETV. See [Section 7.1](#) for details.

d. DOSING & ADMINISTRATION

See [Section 7.0](#) Treatment Plan

e. HOW SUPPLIED

Entecavir is commercially available and will not be supplied. Refer to the current FDA-approved package insert for the most comprehensive and up to date information.

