5.1 Disease Related Criteria

- a. Patients must be diagnosed with Stage I-III solid tumor malignancy. Patients with only carcinoma in situ or with Stage IV disease are excluded.
- b. Patients must not have lymphoma, leukemia, or myeloma.
- c. Patients must not have primary liver cancer, known cirrhosis, or evidence of any malignancy that involves the liver.

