5.2 Prior/Concurrent Therapy Criteria

- a. Patients must be planning to receive systemic anti-cancer therapy (either single agent or some combination of systemic cytotoxic therapy, systemic immunotherapy or systemic targeted therapy) for this solid tumor.
- b. Patients must not have been previously treated with the same anti-cancer therapy regimen that is now anticipated. The anti-cancer therapy does not have to be first-line therapy. Prior and/or concurrent radiotherapy is allowed.
- c. Patients must be registered \leq 28 days prior to the planned start date of anti-cancer therapy. If the patient has started systemic anti-cancer therapy, patient must be registered \leq 42 days after the initiation of first cycle of anti-cancer therapy.
- d. Patients who have received prior anti-cancer therapy must have discontinued all previous therapies (excluding planned anti-cancer therapy to occur in conjunction with this study) \geq 1 day prior to registration to this study.
- e. Patients must not have had any cancer therapy regimen that includes anti-CD20.

- f. Patients must not be receiving antiviral medications active against HBV, including: adefovir, entecavir, lamivudine, telbivudine, tenofovir disoproxil fumarate, tenofovir alafenamide (TAF), or any other FDA approved agents for the treatment of Hepatitis B. Patients who have previously received antiviral medication must not have required any antiviral medication active against HBV \geq 90 days prior to registration to this study.
- g. Patients must not have had hematopoietic stem cell transplantation therapy.
- h. Patients must not be taking or planning to take warfarin.
- i. Patients who will be treated with TAF must not be taking or planning to take oxcarbazepine, phenobarbital, phenytoin, rifabutin, rifampin, rifapentine, or St. John's Wort.

NOTE: Patients taking or planning to take the above listed concomitant medications may be treated with ETV or TDF (instead of TAF).

- j. Patients who will be treated with TAF and are concomitantly taking or plan to take carbamazepine must be given an increased dose of TAF (see Section 7.1) or alternatively be given ETV or TDF.

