7.0 TREATMENT PLAN

For treatment or dose modification questions, please contact [name]., M.P.H., [contact], E-mail: [contact] or [name]., [contact] or E-mail: [contact]. For dosing principles or questions, please consult the SWOG Policy #38 "Dosing Principles for Patients on Clinical Trials" at <http://swog.org> (then click on "Policies & Procedures" under the "About" menu and choose Policy 38).

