7.2 Cohort 1 - Chronic HBV Anti-Viral Treatment

a. Arm 1: Prophylactic Anti-Viral Therapy

The treating investigator and patient will choose the appropriate anti-viral therapy from one of the three anti-viral therapies below. Patients may initiate anti-viral therapy with a reduced dose based on creatinine clearance (see Dose Modifications, [Section 8.2](#))

Start anti-HBV treatment before anti-cancer therapy or up to 42 days after initial anti-cancer therapy. Continue anti-HBV treatment for 6 months after last dose of anti-cancer therapy or for up to 24 months after registration, whichever occurs first.

Agent	Dose	Route	Start Day	Schedule
Tenofovir alafenamide (TAF)	25 mg ^A	PO ^B	As soon as possible after registration; before or up to 42 days after initial dose of anti-cancer therapy	Daily for up to 6 months after the last dose of anti-cancer therapy or maximum of 24 months ^C
Tenofovir disoproxil fumarate (TDF)	300mg PO		As soon as possible after registration; before the last dose or up to 42 days after initial dose of anti-cancer therapy	Daily for up to 6 months after the last dose of anti-cancer therapy or Maximum of 24 months

Entecavir (ETV)	0.5mg	As soon as possible after registration; before the last dose or up to 42 days after initial dose of anti-cancer therapy or anti-cancer therapy.	Daily for up to 6 months after the last dose of anti-cancer therapy or Maximum of 24 months.
--------------------	-------	---	--

^A In patients taking carbamazepine the TAF dose will be increased to 50 mg daily.

^B See dosage administration details in [Section 3.1d](#).

^C Note: Chronic HBV patients should not abruptly stop antiviral therapy after 24 months. Please see [Section 8.2](#) for details on cessation of anti-HBV therapy in chronic HBV patients.

b. Arm 2: Upon Indication Anti-Viral Therapy

The treating investigator and patient will choose the appropriate anti-viral therapy from one of the three anti-viral therapies below. Patients may initiate anti-viral therapy with a reduced dose based on creatinine clearance (see Dose Modifications, [Section 8.2](#)).

Monitor ALT at least every 4 weeks (+/- 2 weeks) as part of trial monitoring for the first 24 weeks, then every 8 weeks thereafter. If hepatitis flare occurs (see definition for hepatitis flare in [Section 10.2b](#)), then obtain an HBV DNA test per usual care. Start anti-HBV therapy if HBV reactivation occurs.

Agent	Dose	Route	Start Day	Schedule

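### Entecavir is set at 0.5 mg daily for Arms 1-3 with no exception for lamivudine-experienced patients; the 1 mg dose appears only in a reference-table footnote that these arms are not directed to (minor dosing-safety gap)

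*Combined protocol and SAP*

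**What the plan says.** Section 3.1d refers entecavir dosing to Section 7.0. There the entecavir rows for Arm 1 (7.2a), Arm 2 (7.2b) and Arm 3 (7.3a) each give 0.5 mg on a daily schedule. The only change to the entecavir starting dose that these sections offer is a reduction for low creatinine clearance. The entecavir table in Section 8.2 begins at 0.5 mg daily for clearance above 50 mL/min. Sections 3, 7 and 8 do not mention prior lamivudine.

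Appendix 18.6 tabulates approved HBV antivirals. Its main entecavir entry is also 0.5 mg daily, but a footnote adds: "Entecavir dose is 1 mg daily if the patient is lamivudine experienced or if they have decompensated cirrhosis".

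Eligibility bears on both triggers in that footnote. Criterion 5.1c reads: "Patients must not have primary liver cancer, known cirrhosis, or evidence of any malignancy that involves the liver". Criterion 5.2f bars current HBV antivirals, lamivudine among them, and then says: "Patients who have previously received antiviral medication must not have required any antiviral medication active against HBV", with a 90-day condition tied to registration.

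For TAF, the same Section 7 tables do carry a dose increase as a footnote: "In patients taking carbamazepine the TAF dose will be increased to 50 mg daily".

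**The concern.** One drug has two doses in one protocol for a patient who can be enrolled. The lower dose stands where an investigator treating a patient in Arms 1-3 will look. The higher one stands in an appendix that nothing in the text for those arms cites.

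What is at stake is the care of individual patients: someone with past lamivudine exposure could be started on, or switched to, entecavir at half the dose the protocol lists for that history. The switch matters because Section 8.2 itself moves patients to entecavir. It names TAF or entecavir as the replacement when TDF is judged to have caused acute kidney injury, and says nothing there about earlier lamivudine.

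**Working it through.** The plan states no statistical figure on this point. The check compares the dosing text across sections and does some simple dose arithmetic.

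**1. Can such a patient be enrolled?**
- Decompensated cirrhosis: known cirrhosis is excluded by 5.1c, so this trigger is closed at entry.
- Prior lamivudine: the wording of 5.2f is awkward, but both readings leave some patients eligible. Read as a 90-day washout, it admits those whose treatment ended earlier. Read literally, it rules out a need for treatment 90 or more days before registration, and so still admits those treated only within the last 90 days who have since stopped.

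**2. Size of the dose difference.**
- Section 7 dose divided by the 18.6 footnote dose: 0.5 / 1 = 0.5.
- Section 3.1b, just after naming a dose range of 0.1 to 1 mg, states: "area under the concentration-time curve (AUC) at steady state increases proportionally to increasing doses of entecavir". Both doses lie in that range, so the exposure ratio is also about 0.5.
- The documents do not translate this into a clinical effect.

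**3. What the 8.2 entecavir table is built on.**

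| Creatinine clearance (mL/min) | Daily dose | Share of 0.5 mg | Interval alternative, per day |
|---|---|---|---|
| >50 | 0.5 mg | 0.5/0.5 = 100% | none |
| 30-50 | 0.25 mg | 0.25/0.5 = 50% | 0.5/2 = 0.25 mg |
| 10-30 | 0.15 mg | 0.15/0.5 = 30% | 0.5/3 = 0.17 mg |
| <10 or dialysis | 0.05 mg | 0.05/0.5 = 10% | 0.5/7 = 0.07 mg |

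Every step is scaled from 0.5 mg and none from 1 mg. A footnote in Section 7 alone would therefore leave the renal rows unanswered.

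**4. Do Arms 1-3 point to Appendix 18.6?** No. The only treatment pointer that fits that table is in 7.3b, for Arm 4, and it cites 18.5, which is the blinded endpoint review.

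**5. How the comparable TAF case is handled.** The carbamazepine increase is 50 / 25 = 2-fold. The entecavir increase is 1 / 0.5 = 2-fold. The first is footnoted in all three tables and repeated in 5.2j and 7.1a. The second appears in none of these places.

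**6. Can every renal case be sent to TAF or TDF under 8.2?** Not quite. TAF needs no adjustment at 15 mL/min or above, but it is not recommended below that without hemodialysis. The TDF table covers 10-29 mL/min and then hemodialysis, with no row for clearance below 10 mL/min without hemodialysis. Criterion 5.3f requires a creatinine clearance but sets no minimum. Any remedy must leave a route for that narrow group.

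**The case against.** The best reply is that Appendix 18.6 is background. It covers children's doses, interferon and non-preferred drugs, gives a link to an outside source, and fits Arm 4, where any approved agent may be used. Its main entecavir entry agrees with Section 7. On this view the protocol does not contradict itself; it leaves a label exception to the label, which is reasonable for marketed drugs that the trial does not supply.

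Several provisions support this. On choice of agent: "The treating investigator and patient will choose the appropriate anti-viral therapy from one of the three anti-viral therapies below". Section 3.1e says: "Refer to the current FDA-approved package insert for the most comprehensive and up to date information"; Sections 3.0 and 8.2 contain similar referrals. Section 7.0 names study contacts and adds: "For dosing principles or questions, please consult the SWOG Policy #38". Section 8.2 leaves treatment and dose changes to the investigator. Section 7.4 recommends contacting study physicians about all HBsAg+ patients, which covers Cohort 1. Harm would need prior lamivudine, entry under 5.2f, entecavir chosen over two alternatives, and none of these sources consulted. In Arms 2 and 3, reactivation must also come first.

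Most of this stands, and it is why the point is minor. It does not close the gap, because every pointer is general and none tells the investigator that prior lamivudine matters. The protocol did not rely on general pointers for the TAF increase.

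A reader might go further and infer that Section 7 and Appendix 18.6 are rival instructions for Arms 1-3, or that the trial underdoses a meaningful share of its antiviral patients and so biases the primary comparisons. The documents support neither. The appendix is not an instruction for those arms. No rate of prior lamivudine use and no share choosing entecavir is given from which a count could be formed.

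**Conclusion.** The point holds as a minor dosing-safety gap that should be fixed. For a lamivudine-experienced patient given entecavir in Arms 1-3, the stated dose is 50% of the one in the appendix footnote, with about 50% of the steady-state exposure.

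This rests on three things: that 5.2f admits at least some such patients, which is true on either reading; that exposure is proportional to dose, as Section 3.1b states; and that the footnote gives the dose intended for these patients. The number affected cannot be estimated from the documents and is probably very small. No material effect on either primary comparison is expected, and sample size, power and alpha are untouched.

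**What to change.** Add one footnote to the entecavir rows in 7.2a, 7.2b and 7.3a, beside the TAF/carbamazepine footnote:

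*Lamivudine-experienced patients should preferably receive TAF or TDF; if entecavir is used, the dose is 1 mg daily (see Appendix 18.6 and the package insert).*

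Add one sentence under the entecavir table in 8.2:

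*The ETV table applies to the 0.5 mg starting dose; for lamivudine-experienced patients with creatinine clearance of 50 mL/min or below, use TAF or TDF where this section gives a dose, otherwise follow the entecavir package insert or ask the dose modification contacts.*

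The last clause is needed for clearance below 10 mL/min without hemodialysis, where Section 8.2 supports neither TAF nor TDF.

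The cost is one footnote repeated in three tables and one sentence. No patients, visits, tests or forms are added.
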